Planned Number of Subjects: Up to 25 subjects (or any number of subjects that can be enrolled by the time of Biologics Licence Application (BLA) submission for PRO 140).	
Indication for Use: PRO 140, in combination with other antiretroviral agents, is indicated for treatment experienced adult HIV-1 patients infected with CCR5-tropic virus. These patients must demonstrate evidence of HIV-1 replication despite ongoing antiretroviral therapy and have documented genotypic or phenotypic resistance to at least one ART drug within three drug classes (or within two or more drug classes with limited treatment option). The options may be limited as a result of drug antiviral class cross-resistance, documented treatment intolerance, documented objective assessments such as renal or hepatic insufficiency (e.g. high creatinine at baseline, limiting treatment options due to potential for toxicity), past adverse reactions such as hypersensitivity reactions or neuropsychiatric issues that could limit use of currently approved drugs.	
Study Population: Study population includes treatment-experienced HIV-infected patients with CCR5-tropic virus who demonstrates evidence of HIV-1 replication despite ongoing antiretroviral therapy with documented genotypic or phenotypic resistance to ART drugs within three drug classes (or within two drug classes with limited treatment option).	
Objectives: The primary objectives of the trial are to assess the efficacy, clinical safety and tolerability parameters of PRO 140 in combination with failing ART during the initial one-week treatment period, and in combination with Optimized Background Therapy during the subsequent 24-week treatment period.	
Endpoints:	
Primary Efficacy Endpoint:	

Name of Sponsor: CytoDyn, Inc.	
Name of Study Product: PRO 140 (Humanized monoclonal antibody to CCR5)	
Protocol Number: PRO 140_CD02_OpenLabel	Therapeutic Indication: Human Immunodeficiency Virus Type-1 (HIV-1) Infection

 Proportion of participants with $\geq 0.5 \log_{10}$ reduction in HIV-1 RNA viral load from baseline at the end of the initial 1-week treatment period 	
Secondary Endpoints: 
 Proportion of participants with $\geq 1 \log_{10}$ reduction in HIV-1 RNA viral load from baseline at the end of the initial 1-week treatment period Mean change from Baseline in HIV-1 RNA levels (\log_{10} copies/mL) at the end of the initial 1-week treatment period Percentage of participants achieving HIV-1 RNA < 400 copies/mL at week 25 Percentage of participants achieving HIV-1 RNA < 50 copies/mL at week 25 Mean change from Baseline in HIV-1 RNA levels (\log_{10} copies/mL) at week 25 Mean change from Baseline in CD4 cell count at the end of the initial 1-week treatment period Mean change from Baseline in CD4 cell count at week 25 	
Safety Assessments: 
 Emergence of Dual/Mixed (D/M)- and CXCR4-tropic virus in patients who had exclusive CCR5-tropic virus at study entry. Tolerability of repeated subcutaneous administration of PRO 140 as assessed by study participants (using Visual Analogue Scale) and by investigator-evaluation of injection site reactions Frequency of treatment-related adverse events resulting in study drug discontinuation Frequency of Grade 3 or 4 adverse events as defined by the DAIDS Adverse Event scale Frequency of treatment-emergent serious adverse events 	
Trial Design: This is a multi-center, two part study, designed to evaluate the safety and tolerability of PRO 140 in conjunction with existing ART (failing regimen) for one week and Optimized Background Therapy (OBT) for 24 weeks. The patient population for this trial are treatment-experienced HIV-infected patients with CCR5-tropic virus and demonstrates evidence of HIV-1 replication despite ongoing antiretroviral therapy with documented genotypic or phenotypic resistance to ART drugs within three drug classes (or within two drug classes with limited treatment option).	
The study is divided into four phases: Screening, Baseline, Treatment, and Follow-up	
Screening Phase (up to 6 weeks): This phase is designed to determine whether subjects are eligible to proceed to the Treatment Phase of the	

Name of Sponsor: CytoDyn, Inc.	
Name of Study Product: PRO 140 (Humanized monoclonal antibody to CCR5)	
Protocol Number: PRO 140_CD02_OpenLabel	Therapeutic Indication: Human Immunodeficiency Virus Type-1 (HIV-1) Infection

study. This phase consists of a series of assessments designed to determine eligibility. A written informed consent from the subject will be obtained by the Investigator or suitably qualified individual before the performance of any protocol-specific procedure.
 
All subjects will continue taking their existing ART (failing regimen) during the Screening Phase, Baseline, and first week (Part 1) of the Treatment Phase.
	

Baseline (1 week):
 
Potentially eligible subjects will confirm continued eligibility one week prior to the first treatment visit. HIV RNA will be tested at Baseline. Subjects whose result is >400 copies/mL will be enrolled one week later. Subjects with results <400 copies/mL will be designated as screen failure. The Baseline Visit (T0) will take place within 6 weeks of the Screening Visit.
	

Treatment Phase (25 weeks ± allowed windows):
 
The Treatment Phase is divided into two parts:
 
 • Part 1: 1-week treatment period consisting of PRO 140 along with existing ART (failing regimen) • Part 2: 24-week treatment period consisting of PRO 140 along with OBT 
The injectable study treatment (PRO 140) will be administered starting at T1 visit and weekly thereafter:
 
 ○ by a qualified medical professional (MD, DO, PA, LPN, LVN, NP, RN, or CMA if permitted by state law) or ○ self-administered by subjects 
Subjects will receive PRO 140 700 mg administered subcutaneously once per week.
 
Note: Subjects who are currently enrolled and receiving 350 mg dose will have the option to move to the 700 mg dose for the remainder of their participation in the trial.
 
Note: Study treatment injections at T1, T2, T3, T7, T11, T15, T19 and T23 must be administered at clinic. The remaining study treatment injections may be self-administered by subjects outside the clinic.
 
Part 1: One-week treatment period [PRO 140 + existing ART]
 
Part 1 of treatment phase begins with an evaluation of results of laboratory samples collected at the Screening Visit. All subjects who fail to meet eligibility criteria will be considered screen failures and exit the study without further evaluation. Subjects who meet all eligibility criteria, as per data gathered from Screening Visit, will be enrolled and receive PRO 140 for one week (Table 0-1). A visit to confirm HIV RNA continues to meet eligibility will be conducted one week prior to the first treatment.
 
Table 0-1: One-week period [PRO 140 + existing ART]
	

Name of Sponsor: CytoDyn, Inc.				
Name of Study Product: PRO 140 (Humanized monoclonal antibody to CCR5)				
Protocol Number: PRO 140_CD02_OpenLabel	Therapeutic Indication: Human Immunodeficiency Virus Type-1 (HIV-1) Infection			
Study Drug	Dosage Form	IP concentration	Dosing Frequency and Amount	Route of Administration
PRO 140	Parenteral solution	175 mg/mL	2 injections of PRO 140 (2 X 2 mL/inj.) at T1 visit	SC injection

Part 2: 24-week treatment period [PRO 140 + OBT]

As shown in Table 0-2, after 7 days all subjects will enter the 24-week treatment period. During this period, all subjects will receive PRO 140 SC injection and Optimized Background Therapy. Optimized Background Therapy (OBT) is a standard-of-care regimen comprised of 3 or more antiretroviral agents selected by the investigator based on treatment history and genotypic and/or phenotypic assessments.

Table 0-2: 24-week treatment period [PRO 140 + OBT]

Study Drug	Dosage Form	IP concentration	Dosing Frequency and Amount	Route of Administration
PRO 140	Parenteral solution	175 mg/mL	2 injections of PRO 140 (2 X 2 mL/inj.) per week for up to 24 weeks (T2 – T25)	SC injection

Study participants will be regularly monitored for viral load following initiation of PRO 140, and will cease weekly study treatment injections should they experience treatment failure.

Subjects who experience treatment failure at any point during the Treatment Phase will undergo the Treatment Failure (TF) Visit assessments and then return in 4 weeks (\pm allowed window) for the Safety Follow-up Visit.

Treatment failure is defined in terms of virologic non-response and virologic rebound in the Open-Label Treatment Phase of the study.

(1) *Virologic non-response is defined as two consecutive viral load results of:*

- $< 0.5 \log_{10}$ copies/mL decrease in HIV-1 RNA at Day 7 of Treatment Phase Part 2. [Assessment Timepoint: T3 and T4 visit]
- $< 1.0 \log_{10}$ copies/mL decrease in HIV-1 RNA at or after Week 4 of Treatment Phase Part 2 unless HIV-1 RNA < 400 copies/mL [Assessment Timepoint: from T6 up to T25 visit].
- *Confirmed plasma HIV-1 RNA levels ≥ 400 copies/mL at Week 25 of Treatment Phase Part 2. [Assessment Timepoint: T25 visit]*

(2) *Virologic rebound is defined as two consecutive viral load results of:*

- $\geq 1.0 \log_{10}$ copies/mL increase in plasma HIV-1 RNA above nadir level* in Treatment Phase Part 2 [Assessment Timepoint: from T3 up to T25 visit] or

**Note: This refers to "Nadir" level in the Treatment Phase which starts from T2 visit*

Name of Sponsor: CytoDyn, Inc.	
Name of Study Product: PRO 140 (Humanized monoclonal antibody to CCR5)	
Protocol Number: PRO 140_CD02_OpenLabel	Therapeutic Indication: Human Immunodeficiency Virus Type-1 (HIV-1) Infection

 • ≥ 400 copies/mL after suppression to < 50 copies/mL in Treatment Phase Part 2. [Assessment Timepoint: from T3 up to T25 visit] 	
Safety Follow-up Visits: 
Duration of the Follow-up Phase is determined upon whether or not subject has experienced treatment failure during the Open-Label Treatment Phase.
 
 • Subjects who experience treatment failure within Treatment Phase Part 2 will be followed up every 4 weeks until viral suppression is achieved (i.e., plasma HIV-1 RNA levels below level of detection) or upto a maximum of 6 months after cessation of therapy if the treating physician does not feel that there is an antiretroviral regimen that will regain full viral suppression. • Subjects who do not experience treatment failure at the end of Treatment Phase Part 2, will be followed up every 2 weeks for total of 4 weeks. 	
Duration of Study: 
 • Screening Phase: 
 ○ up to 6 weeks* 
*Subject will move to Treatment Phase as soon as HIV-1 viral tropism, genotypic and phenotypic resistance results are available for review by Investigator, within 6 weeks of the Screening Visit.
 • Baseline 
 ○ 1 week • Treatment Phase: 
 ○ 25 weeks (\pm allowed windows) • Follow-up Phase: 
 ○ 4 weeks** (\pm allowed windows) 
 **or up to maximum of 6 months after experiencing Treatment Failure (TF) if the treating physician does not feel that there is an antiretroviral regimen that will regain full viral suppression. • Total Study Duration: 
 ○ 36 weeks [Does not include additional follow-up time for treatment failure subjects] 	
Inclusion Criteria: Potential subjects are required to meet all of the following criteria for enrollment into the study. 
 1. Males and females, age ≥ 18 years 2. Exclusive CCR5-tropic virus at Screening Visit as determined by Monogram Biosciences Trofile® Assay 	

Name of Sponsor: CytoDyn, Inc.	
Name of Study Product: PRO 140 (Humanized monoclonal antibody to CCR5)	
Protocol Number: PRO 140_CD02_OpenLabel	Therapeutic Indication: Human Immunodeficiency Virus Type-1 (HIV-1) Infection

3. Have a history of at least 3 months on current antiretroviral regimen
 
4. Treatment-experienced HIV-infected patients with documented genotypic or phenotypic resistance to at least one ART drug within three drug classes
 
OR
 
Treatment-experienced HIV-infected patients with documented genotypic or phenotypic resistance to at least one ART drug within two drug classes and have limited treatment option. The options may be limited as a result of drug antiviral class cross-resistance, documented treatment intolerance, documented objective assessments such as renal or hepatic insufficiency (e.g. high creatinine at baseline, limiting treatment options due to potential for toxicity), past adverse reactions such as hypersensitivity reactions or neuropsychiatric issues that could limit use of currently approved drugs.
 
5. Be willing to remain on treatment without any changes or additions to the OBT regimen, except for toxicity management or upon meeting criteria for treatment failure
 
6. Plasma HIV-1 RNA \geq 400 copies/mL at Screening Visit as determined by Human Immunodeficiency Virus 1 (HIV-1) Quantitative, RNA (Roche Taqman® Real-Time PCR) and documented detectable viral load (HIV-1 RNA >50 copies/ml) within the last 3 months prior to Screening Visit.
 
7. Laboratory values at Screening of:
 
 Absolute neutrophil count (ANC) \geq 750/mm³ Hemoglobin (Hb) \geq 10.5 gm/dL (male) or \geq 9.5 gm/dL (female) Platelets \geq 75,000 /mm³ Serum alanine transaminase (SGPT/ALT) $<$ 5 x upper limit of normal (ULN) Serum aspartate transaminase (SGOT/AST) $<$ 5 x ULN Bilirubin (total) $<$ 2.5 x ULN unless Gilbert's disease is present or subject is receiving atazanavir in the absence of other evidence of significant liver disease Creatinine \leq 1.5 x ULN 
8. Clinically normal resting 12-lead ECG at Screening Visit or, if abnormal, considered not clinically significant by the Principal Investigator
 
9. Both male and female patients and their partners of childbearing potential must agree to use 2 medically accepted methods of contraception (e.g., barrier contraceptives [male condom, female condom, or diaphragm with a spermicidal gel], hormonal contraceptives [implants, injectables, combination oral contraceptives, transdermal patches, or contraceptive rings], and intrauterine devices) during the course of the study (excluding women who are not of childbearing potential and men who have been sterilized).
	

Name of Sponsor: CytoDyn, Inc.	
Name of Study Product: PRO 140 (Humanized monoclonal antibody to CCR5)	
Protocol Number: PRO 140_CD02_OpenLabel	Therapeutic Indication: Human Immunodeficiency Virus Type-1 (HIV-1) Infection

Females of childbearing potential must have a negative serum pregnancy test at Screening visit and negative urine pregnancy test prior to receiving the first dose of study drug.
 
10. Willing and able to participate in all aspects of the study, including use of SC medication, completion of subjective evaluations, attendance at scheduled clinic visits, and compliance with all protocol requirements as evidenced by providing written informed consent.
 
Note: Subjects diagnosed with either substance dependence or substance abuse or any history of a concomitant condition (e.g., medical, psychologic, or psychiatric) may be enrolled if in the opinion of site investigator these circumstances would not interfere with the subject's successful completion of the study requirements.
	

Exclusion Criteria: Potential subjects meeting any of the following criteria will be excluded from enrollment.
 
 1. Documented CXCR4-tropic virus or Dual/Mixed tropic (R5X4) virus as determined by HIV-1 tropism assay 2. Patients with no viable treatment options (i.e., no fully active antiretroviral drug available which can be effectively combined to form a viable new OBT) 3. Any active infection or malignancy requiring acute therapy (with the exception of local cutaneous Kaposi's sarcoma) 
Note: Subjects infected by the hepatitis B virus or hepatitis C virus will be eligible for the study if they have no signs of hepatic decompensation and meet the liver function tests eligibility criteria.
 
 4. Laboratory test values of \geq grade 3 DAIDS laboratory abnormality with the exception of the absolute CD4+ count criterion of $< 200/\text{mm}^3$ 5. Females who are pregnant, lactating, or breastfeeding, or who plan to become pregnant during the study 6. Unexplained fever or clinically significant illness within 1 week prior to the first study dose 7. Any vaccination within 2 weeks prior to the first study dose. 8. Subjects weighing $< 35\text{kg}$ 9. History of anaphylaxis to oral or parenteral drugs 10. History of Bleeding Disorder or patients on anti-coagulant therapy 11. Participation in an experimental drug trial(s) within 30 days of the Screening Visit 12. Any known allergy or antibodies to the study drug or excipients 13. Treatment with any of the following: 	

Name of Sponsor: CytoDyn, Inc.	
Name of Study Product: PRO 140 (Humanized monoclonal antibody to CCR5)	
Protocol Number: PRO 140_CD02_OpenLabel	Therapeutic Indication: Human Immunodeficiency Virus Type-1 (HIV-1) Infection

a. Radiation or cytotoxic chemotherapy with 30 days prior to the Screening Visit
 
b. Immunosuppressants within 60 days prior to the Screening Visit
 
c. Immunomodulating agents (e.g., interleukins, interferons), hydroxyurea, or foscarnet within 60 days prior to the Screening Visit
 
d. Oral or parenteral corticosteroids within 30 days prior to the Screening Visit. Subjects on chronic steroid therapy > 5 mg/day will be excluded with the following exception:
 
 ○ Subjects on inhaled, nasal, or topical steroids will not be excluded. 
14. Any other clinical condition that, in the Investigator's judgment, would potentially compromise study compliance or the ability to evaluate safety.
	

Statistical Considerations:
 
Sample Size Determination and Rationale:
 
Up to 25 subjects (or any number of subjects that can be enrolled by the time of BLA submission for PRO 140) will be enrolled. The sample size is based on clinical judgement with an intention to supplement the data for the target BLA indication.
 
Analysis Populations:
 
The Intent-to-Treat (ITT) population is defined as the set of subjects who are enrolled and have received at least one dose of PRO 140.
 
Subjects who discontinue from the study prior to their first post-baseline assessment will be included in the ITT population and analyzed as non-responders in the primary analysis.
 
The Per Protocol (PP) population is defined as the set of subjects who meet the ITT population requirements, and were not associated with a major protocol violation. This population will be identified before the database lock.
 
The Safety population is defined as all subjects who received at least one dose of PRO 140. This population will be used for the analysis of safety parameters.
 
Efficacy Analysis
 
The primary analysis of primary and secondary endpoint will be conducted on the ITT population and PP population will be used for supportive analysis using the same analysis methodologies.
 
All data collected from the study will be presented as a by-subject listing and also summarized according to the variable type as:
	

Name of Sponsor: CytoDyn, Inc.	
Name of Study Product: PRO 140 (Humanized monoclonal antibody to CCR5)	
Protocol Number: PRO 140_CD02_OpenLabel	Therapeutic Indication: Human Immunodeficiency Virus Type-1 (HIV-1) Infection

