4 STUDY SCHEDULE

As shown in [Figure 4-1](#), this study is divided into three phases: Screening, Treatment and Follow-up.

Figure 4-1: Study Schematic

(1) **Screening Phase:** This phase lasts up to 6 weeks, consists of Screening Visit (SV) and begins with signing of Informed Consent. Assessments performed during this phase determine the subject's final eligibility for study participation. First treatment will be administered within 42 days of Screening Visit.

All subjects will continue taking their existing ART (failed regimen) during the Screening Phase and first week of the Treatment Phase (Part 1).

(2) **Baseline:** The Baseline (T0) visit will take place within 6 weeks of the Screening Visit, as soon as HIV-1 viral tropism, genotypic and/or phenotypic resistance results are available for review by Investigator. HIV RNA and TruCount Assay will be performed to ensure continued eligibility prior to the first Treatment Visit (T1).

(3) **Treatment Phase:** Subjects will receive up to 25 treatments, given approximately every week (window period of ± 3 days) or until treatment failure is experienced, whichever comes first.

The first Treatment Visit (T1) will take place within one week of the T0 visit.

The injectable study treatment (PRO 140) will be administered by a qualified medical

professional (MD, DO, PA, LPN, LVN, NP, RN, or CMA if permitted by state law) or self-administered by subjects.

Note: *Study treatment injections at T1, T2, T3, T7, T11, T15, T19 and T23 must be administered at clinic. The remaining study treatment injections may be self-administered by subjects outside the clinic.*

Any time during Treatment Period Part 2, if treatment failure occurs, Investigator will readjust antiretroviral regimen based on HIV-1 genotypic and/or phenotypic drug resistance results obtained during the TF visit.

Subjects will be allowed to continue PRO 140 with existing OBT regimen while waiting for new regimen to be constructed by the Investigator.

Treatment failure is defined in terms of virologic non-response and virologic rebound in Part 2 of the Treatment Phase of the study:

a) Virologic non-response is defined as two consecutive viral load results of:

- $<0.5 \log_{10}$ copies/mL decrease in HIV-1 RNA at Day 7 of Treatment Period Part 2. *[Assessment Timepoint: T3 visit]*

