- Anytime during the Treatment Phase, if treatment failure occurs or have met any other criteria for discontinuation of study treatment as specified in [section 5.2.1](#) of the protocol. Subjects

will be allowed to continue PRO 140 with existing OBT regimen while waiting for new regimen to be constructed by the Investigator.

Note:

- Subjects may return to clinic for an additional blood draw in-between the clinic visits for plasma HIV-1 RNA levels, per the discretion of the Investigator.
- Subjects who experience treatment failure at any time during the Treatment Phase will undergo the Treatment Failure (TF) Visit assessments and enter the Follow-up Phase of the study.
- Subjects who meet any criteria (other than treatment failure) for discontinuation of study treatment as specified in [section 5.2.1](#) of the protocol, will undergo End of Treatment Phase (EOT) Visit assessments and enter the Follow-up Phase of the study.
- Subjects who do not experience treatment failure will enter the Follow-up Phase of the study at the end of 25-week Treatment Phase.

Visits during the Treatment Phase will commence on T1, i.e. the date of first treatment, with weekly visits (\pm 3 days) thereafter. The first Treatment Visit (T1) will take place as soon as HIV-1 viral tropism, genotypic and/or phenotypic resistance results are available for review by Investigator, within 6 weeks of the Screening Visit.

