OBT is a standard-of-care regimen comprised of 3 or more antiretroviral agents selected by the investigator based on treatment history and genotypic and/or phenotypic assessments. The use of another experimental agent (e.g., ibalizumab) to create a viable HIV suppressive OBT regimen in certain subjects with severely limited approved and available therapeutic options will be allowed with the prior approval from sponsor.

4.3.2 Treatment Visit-2 (T2) to Treatment Visit-25 (T25) - Part 2 of Treatment Phase

The following assessments will be performed at each visit, unless otherwise specified:

- Assess for any Adverse Events and changes in Concomitant medications (see [section 9](#) and [7.5](#)),
- Symptom-directed physical examination (see [section 7.7](#)),
- Neurological Assessment (see [section 7.9](#))
 - **Note:** *Neurological assessment will be performed at T3, T7, T11, T15, T19, T23 visits*
- Vital Signs (see [section 7.10](#))
 - **Note:** *Post-treatment vital signs will be assessed within 15 minutes following study treatment administration when performed inside clinic.*
- Collection of Blood Specimens (see [section 7.11](#)) for
 - Plasma HIV-1 RNA level
 - TruCount T Assay
 - HIV-1 Drug Resistance Assay
 - PK sample for PRO 140
 - Serum concentration of ART drugs
 - Anti-idiotypic antibodies to PRO 140
 - **Note:** *Blood sample for Plasma HIV-1RNA level, TruCount T Assay, and HIV-1 Drug Resistance Assay will be performed at SV, T1, T2, T3, T7, T11, T15, T19, T23, EOT and TF visits*
 - **Note:** *PK sample for PRO 140 and Anti-idiotypic antibodies to PRO 140 will be performed at T1, T7, T15, EOT and TF visits*

- **Note:** Serum concentration for ART will be performed at T1, T7, T15, visits, EOT and TF visits, as well as any Unscheduled Visit within the Treatment Phase as per discretion of the investigator.
- Study Treatment Administration (PRO 140)
- Injection Site Reaction Assessment (see [section 7.13](#))
 - **Note:** To assess injection site reactions, the investigator will use the DAIDS AE grading table (refer to [section 16.3](#)).
- Subject-perceived Injection Site Pain Assessment (see [section 7.14](#))
 - **Note:** Subject-perceived injection site pain will be assessed using the Pain Visual Analog Scale (VAS) prior to study treatment administration assessing average pain at injection site since last treatment.

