4.3.4 Treatment Failure (TF) Visit

Treatment failure is defined in terms of virologic non-response and virologic rebound in Part 2 of the Treatment Phase:

(1) Virologic non-response is defined as two consecutive viral load results of:

- $<0.5 \log_{10}$ copies/mL decrease in HIV-1 RNA at Day 7 of Treatment Phase Part 2. *[Assessment Timepoint: T3 visit]*
- $<1 \log_{10}$ copies/mL decrease in HIV-1 RNA at or after Week 4 of Treatment Phase Part 2 unless HIV-1 RNA <400 copies/mL. *[Assessment Timepoint: from T6 up to T25 visit]*
- Confirmed plasma HIV-1 RNA levels ≥ 400 copies/mL at Week 24 of Treatment Phase Part 2. *[Assessment Timepoint: T25 visit]*

(2) Virologic rebound is defined as two consecutive viral load results of:

$\geq 1.0 \log_{10}$ copies/mL increase in plasma HIV-1 RNA above nadir level* in Treatment Phase Part 2 *[Assessment Timepoint: from T3 up to T25 visit]* or

*Note: This refers to “Nadir” level in Treatment Phase Part 2 which starts from T2 visit.

- ≥ 400 copies/mL after suppression to <50 copies/mL in Treatment Phase Part 2. *[Assessment Timepoint: from T3 up to T25 visit]*

The following assessments will be performed for subjects who experience treatment failure at any time during the Treatment Phase:

- Assess for any Adverse Events and changes in Concomitant medications (see [section 9](#) and [7.5](#)),
- Complete Physical Examination (see [section 7.7](#)),
- Vital Signs (see [section 7.10](#)),
- Neurological Assessment (see [section 7.9](#)),
- Subject-perceived Injection Site Pain Assessment (see [section 7.14](#)),
- Collection of Blood Specimens (see [section 7.11](#)) for
 - Plasma HIV-1 RNA level
 - TruCount T Assay
 - Complete Blood Count
 - Biochemistry
 - HIV Drug Resistance Assay
 - HIV PhenoSense Entry® Assay
 - HIV Trofile® Assay

- Anti-idiotypic antibodies to PRO 140
- PK sample for PRO 140
- Serum Conc. of ART drugs
- Blood sample collection for Exploratory/Confirmatory analysis
- Change in Optimized Background Therapy based on genotypic and phenotypic results obtained at TF visit.

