4.5 UNSCHEDULED VISITS

In the event that the patient returns to clinic at a time other than a regularly scheduled study visit, the visit will be regarded as an unscheduled visit. Assessments at unscheduled visits are at the discretion of the Investigator.

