7.11.7 Plasma HIV-1 RNA level and TruCount T Assay

- Frequency of testing: At SV, Treatment Visits 1, 2, 3, 7, 11, 15, 19 and 23, as well as EOT and TF visits. In addition, blood sample will also be collected at all Treatment Failure Follow-up (TF-FU) Visits or Non-Treatment Failure Follow-up (NTF-FU) Visits.
- To assess antiretroviral therapeutic response to PRO 140

Note: *Plasma HIV-1 RNA level will be measured using Human Immunodeficiency Virus 1 (HIV-1), Quantitative, RNA (Abbott RealTime) test.*

TruCount T Assay includes measurement of Absolute Lymphocytes, CD3 cell count, CD4 cell count, CD8 cell count, CD3%, CD4% and CD8%

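### Day-7 non-response needs two consecutive viral loads, but no RNA draw is scheduled between T3 and T7; the final ≥400 copies/mL criterion also names a visit (T25) without a draw

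*Protocol*

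**What the plan says.** Treatment failure is defined in four places: the synopsis, section 4, section 4.3.4 and section 5.2.1. Each requires two consecutive viral load results for non-response.

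- **Day-7 criterion (<0.5 log10 decrease).** The synopsis has "copies/mL decrease in HIV-1 RNA at Day 7 of Treatment Phase Part 2. [Assessment Timepoint: T3 and T4 visit". The three body sections have "Assessment Timepoint: T3 visit".
- **Final criterion (confirmed ≥400 copies/mL).** All four places name T25. The synopsis has "copies/mL at Week 25 of Treatment Phase Part 2. [Assessment Timepoint: T25 visit". Section 4 counts Week 25 from the start of the treatment period, and sections 4.3.4 and 5.2.1 say Week 24 of Part 2.
- **RNA schedule.** Section 4.3.2 says that the samples "will be performed at SV, T1, T2, T3, T7, T11, T15, T19, T23, EOT and TF visits". Section 7.11.7 agrees: "At SV, Treatment Visits 1, 2, 3, 7, 11, 15, 19 and 23, as well as EOT and TF visits".
- **Clinic visits.** Section 4 states: "Study treatment injections at T1, T2, T3, T7, T11, T15, T19 and T23 must be administered at clinic". T4 and T25 may therefore be home injections.
- **Extra draws.** Section 4.3 allows an "additional blood draw in-between the clinic visits for plasma HIV-1 RNA levels, per the discretion of the Investigator", and section 4.5 adds: "Assessments at unscheduled visits are at the discretion of the Investigator".

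**The concern.** A stopping rule based on two consecutive results needs two draws at the visits it names. The Day-7 rule has one under either wording: T4 has no scheduled RNA, and a single visit (T3) cannot supply two consecutive results.

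Failure status governs care. Inclusion criterion 5 commits subjects to an unchanged OBT except for toxicity or once failure criteria are met. Under section 5.2.1, any other wish to adjust OBT is itself a reason to stop PRO 140. Failure also opens the TF visit and the longer follow-up track. If confirmation depends on whether an investigator happens to order a draw, two subjects with the same T3 result can be classified at different times. The protocol plans up to 25 subjects at up to 40 centers, so local habit could matter.

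The final criterion raises a smaller version of the same question: no RNA is drawn at T25, and nothing says what follows a first value ≥400 copies/mL at EOT.

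**Working it through.** The protocol gives no figure to reproduce, so the check sets each criterion against the RNA schedule.

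**Inputs**
- Part 2 RNA draws: T2, T3, T7, T11, T15, T19, T23 and EOT (sections 4.3.2 and 7.11.7). The TF visit also draws RNA, but only for subjects already classed as failures (4.3.4).
- Visits are weekly ±3 days (Table 4-1), so one interval is 7 days, range 4–10.
- NTF-FU1 is 14 ±3 days after EOT (Table 4-2).
- Assumption: EOT is one week after T25. The protocol gives no explicit EOT window.

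**Step 1: visit timing.** Elapsed week of Part 2 at visit Tk = k − 2. This gives T3 = 1 (Day 7), T4 = 2, T6 = 4, T7 = 5, T11 = 9, T23 = 21, T25 = 23 and EOT = 24. The count reproduces the protocol's own pairings of Day 7 with T3 and Week 4 with T6.

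**Step 2: scheduled draws in each window, counting EOT**

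| Criterion | Draws | Consecutive pairs |
|---|---|---|
| <0.5 log10, T3 and T4 (synopsis) | 1 (T3) | 0 |
| <0.5 log10, T3 (body) | 1 (T3) | 0 |
| <1.0 log10, T6–T25 | 6 | 5 |
| ≥400 at the end of Part 2 | 1 (EOT; none at T25) | 0, or 1 if T23 is the first of the pair |
| Each rebound criterion, T3–T25 | 7 | 6 |

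**Step 3: ways to complete the Day-7 pair.** T3 to T7 is 4 × 7 = 28 days (4 × 4 = 16 to 4 × 10 = 40).

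| Reading | Delay after T4 | Status |
|---|---|---|
| T3 + T4 | none | T4 draw is discretionary |
| T2 + T3 | none | scheduled, but stated nowhere |
| T3 + T7 | 3 × 7 = 21 days (12–30) | T7 is not a named visit and falls under the 1.0 log10 criterion |
| T7 + T11, 1.0 log10 criterion | 7 × 7 = 49 days (28–70) | scheduled and stated |

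T2 is Day 0 of Part 2. Its viral load reflects one week of PRO 140 on the failing regimen, before OBT has acted.

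**Step 4: the final criterion's label.** Part 2 has 24 weeks and 24 treatment visits (T2–T25). A Week 25 of Part 2 does not exist whether weeks are counted as elapsed time (EOT = 24) or by visit order (T25 = 24th). On elapsed time, the other three statements point to EOT, given the assumption above. By visit order they could point to T25, which has no draw.

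**Step 5: confirming the final criterion.** T23 to EOT is 3 × 7 = 21 days (12–30), and both draw RNA. What remains is a subject with T23 <400 and EOT ≥400. That subject's next scheduled RNA is NTF-FU1, 11–17 days after EOT.

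**The case against.** The strongest reply on the Day-7 rule is that the body text can be met from scheduled draws by pairing T2 with T3, with no delay. That is arithmetically right and belongs among the readings. It does not cure the rule: no section states it, the synopsis names T4, and the T2 value says nothing about response to OBT.

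It can also be said that section 4.3 permits an interim draw, that the synopsis tells the investigator when to take it, and that section 5.2 lets the investigator discontinue a subject at any time if medically necessary. All true, and it limits the harm. But the rule then works only through discretion.

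A reader might infer that early non-responders escape detection. The documents do not support that: a persistent non-responder meets the 1.0 log10 criterion from T7 and T11. The effect is delay, not loss.

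A reader might also treat the final criterion as equally unworkable. It is not. T23 plus EOT can satisfy it, any two-result rule leaves a first high value at the last visit unconfirmed, and an RNA draw is scheduled at NTF-FU1. What is missing is a statement of whether that draw confirms failure and triggers the TF visit. Nor can the lack of later tropism data be laid mainly on this gap: Trofile is scheduled only at screening and TF, so every subject without failure lacks a later result by design.

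**Conclusion.** The Day-7 non-response rule is wrong as written. It cannot be met at its named visits without a discretionary draw, and the synopsis and body disagree on which visits those are. Without such a draw, and leaving aside the unstated T2 + T3 reading, confirmation falls about 3 weeks (T7 accepted) or about 7 weeks (T7 and T11 needed) after T4. These delays are upper bounds on extra PRO 140 dosing, since dosing may continue while a new regimen is built. Classification also becomes investigator-dependent.

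The T25 criterion is a secondary error: a visit without a draw, an impossible week label in the synopsis, and no rule for a first high value at EOT. Equating the other labels with EOT rests on the assumed EOT date and on elapsed counting.

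The documents give no basis for the number of subjects affected. The inference that efficacy results are compromised is not supported: no primary or secondary endpoint is defined by confirmed failure.

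**What to change.** Amend the protocol; an analysis plan cannot add a blood draw.

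1. State the failure definition once and cross-refer to it elsewhere.
2. Day 7: require a repeat RNA at T4 only when T3 shows a decrease below 0.5 log10, and define the pair as T3 plus that repeat.
3. Final criterion: name EOT instead of T25 and correct the synopsis label to Week 24 of Part 2. Say when EOT occurs relative to T25.
4. Accept T23 and EOT both ≥400 copies/mL as confirmation. Otherwise require a repeat after a first EOT value ≥400: preferably a prompt draw, at the least the NTF-FU1 draw with its role stated. If confirmed, perform the TF-visit assays (Trofile, PhenoSense Entry, resistance).

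The cost is amendment wording and one extra blood draw or clinic visit for each subject with a triggering value; using NTF-FU1 in item 4 adds no visit. Other subjects are unaffected, and T4 can remain a home injection for them.
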